2.2.3. Exploratory Endpoints

- Changes in REVEAL 2.0 risk score at Week 12 compared with baseline

3. INVESTIGATIONAL PLAN

3.1. Overall Study Design and Plan

This is a Phase 1b randomized, double-blind, placebo-controlled, on top of background therapy, dose escalation study to assess safety, efficacy and PK of GMA301 in subjects with PAH. The study will be carried out at sites in China and the US.

After signing informed consent, subjects will participate in a Screening Phase. The subjects' medical history will be obtained through interview and a chart review before the subject undergoes a physical examination.

Subjects will be selected and enrolled from the PAH population who are taking local-approved, non-ERA agents, including but not limited to calcium channel blockers, phosphodiesterase type 5 inhibitors, guanylate cyclase stimulators, non-intravenous prostacyclin receptor agonists and prostacyclin analogues.

The dosage of PAH medication must be stable for 3 months before Screening.

Subjects who underwent RHC within the 3 months prior to Screening will not be required to repeat another RHC if the investigators accept the quality of the saved waveforms and pressure measurements and these meet study entry criteria.

Subjects meeting screening criteria for baseline metrics will then be randomized by Interactive Web Response System (IWRS). Each treatment cohort will be randomized at a 3:1 ratio of active treatment to placebo in each cohort. Subjects will be randomized to receive either:

- Q4W GMA301 IV injections
 - or
 - Q4W placebo IV injections (indistinguishable from GMA301).

Subjects will be sequentially recruited into 3 ascending dose treatment cohorts with GMA301-assigned subjects receiving either 300, 600 or 1000 mg injections of the study drug depending on their assigned cohort. Each cohort will contain 12 subjects, 9 of whom will be administered active GMA301 and 3 of whom will be administered placebo. All subjects will undergo IV injection at baseline, Week 4, and Week 8.

Dosing will proceed in a cohort-based dose escalation sequence from 300 mg GMA301 in the initial cohort. Pre-specified criteria for dose escalation based on subjects' safety will be assessed by a Safety Review Committee (SRC) before progressing to the next higher dose level as described below. The efficacy parameters will include disease-relevant hemodynamic parameters derived from RHC, REVEAL 2.0 risk score, WHO functional class, ECG, 6MWT, biomarkers and echocardiography measures of right ventricular function.

All key efficacy parameters will be assessed at 4, 8, and 12 weeks following baseline evaluation and an ECG will be performed as scheduled. The protocol will include a

6-week follow-up (from Week 12 to Week 18) at which time subjects will be assessed to identify any AEs and conducting the PK assessment.

Routine clinical and laboratory parameters including antigenicity and AE reporting will be examined.

Overall, 36 subjects, with 3 cohorts each composed of 12 subjects, will participate in a multiple-dose, sequential-group fashion. An overview of the study design is shown in [Figure 1](#) and the planned dose levels in [Figure 2](#).

The total duration of the study for an individual subject will be approximately 22 weeks including up to 4 weeks of screening, 12 weeks of double-blind treatment period, and 6 weeks of follow-up. During the double-blind treatment period (12 weeks), the subjects will receive the IV injections at Week 0 (baseline), Week 4, and Week 8, respectively.

[figure not shown]

Figure 1: Study Schematic

[figure not shown]

Figure 2: Planned Dose Levels

A Schedule of Assessments is presented in [Appendix 6](#).

3.2. Study Start and End of Study Definitions

The start of the study is defined as the date the first enrolled subject signs an Informed Consent Form (ICF). The point of enrollment occurs at the time of the subject number allocation. The end of the study is defined as the date of the last subject's last assessment (scheduled or unscheduled).

3.3. Discussion of Study Design, Including the Choice of Control Groups

A sequential-group, ascending-dose design has been chosen for safety reasons as GMA301 is in the early stage of clinical development. Intravenous doses have been chosen for the study, as this is the intended clinical route of administration.

Based upon the nonclinical data, the duration of each treatment period is considered adequate to achieve the study objectives. Details of the dosing regimen and duration used for the study will be documented in the trial master file (TMF).

The selection of the GMA301 dosing frequency of Q4W via IV injection at baseline and then at Week 4 and Week 8 was based on the available clinical safety, tolerability and PK data obtained from healthy human subjects.¹⁸

To estimate and determine the levels and frequency of GMA301 dosing for the upcoming Phase Ib study, a simulation of GMA301 for a Q4W repeated dosing in human subjects has been established based on all previous observations in cynomolgus monkeys and healthy human volunteers. The simulation indicated that a steady state could be achieved after the 3rd dose, and the Q4W dose interval has been deemed safe for human subjects.

3.4. Dose selection in the Study

GMA301 300, 600 and 1000 mg IV injection Q4W for 3 months was based on the available clinical safety, tolerability and PK data obtained from healthy human subjects.

The proposed GMA301 dose levels are shown in [Table 2](#).

Table 2: Proposed Investigational Medicinal Product Dose Levels

Cohort	Intervention	Treatment
1	300 mg GMA301 (N=9)	Drug: GMA301, 300 mg IV Q4W at Week 0 (baseline), Weeks 4 and 8
	Placebo (N=3)	Drug: Placebo, IV, Q4W at Week 0 (baseline), Weeks 4 and 8
2	600 mg GMA301 (N=9)	Drug: GMA301 600 mg IV, Q4W at Week 0 (baseline), Weeks 4 and 8
	Placebo (N=3)	Drug: Placebo IV, Q4W at Week 0 (baseline), Weeks 4 and 8
3	1000 mg GMA301 (N=9)	Drug: GMA301 1000 mg IV, at Week 0 (baseline), Weeks 4 and 8
	Placebo(N=3)	Drug: Placebo IV, Q4W at Week 0 (baseline), Weeks 4 and 8

Details of all doses administered in the study will be documented in the TMF.

3.5. Safety Review Committee (SRC)

A SRC will be established to assess safety profile for each cohort to determine dose escalation. The SRC will be composed of 3 investigators, the Covance Lead Project Physician, the Gmax Lead Project Physician, and another unblinded physician who is not involved in this study.

SRC Operation. The SRC will meet after 8 of 12 subjects have received 3 doses of the study drug with a 28-day follow-up and the entire cohort of 12 subjects has been randomized.

The initial SRC meeting will review safety data from the initial 8 subjects in Cohort 1 who have completed 3 doses of the study drug and have been followed for 28 days following the third dose. Upon SRC's approval, Cohort 2 will be opened for recruitment once the residual 4 subjects have been randomized in Cohort 1. The second meeting of the SRC will review safety data from the initial 8 subjects in Cohort 2 **and the 4 residual subjects from Cohort 1 who were not yet reviewed.** Upon SRC's approval, once the residual 4 subjects in Cohort 2 are randomized, Cohort 3 can be initiated for recruitment. If fewer than 8 subjects (including 8) in a cohort have completed administration and follow-up regimen, with some drop-outs, their safety data will be reviewed by SRC aiming to determine whether the next cohort with a higher dose can be started. Additionally, ad hoc meetings will be organized in case of any SAE or adverse event with maximum severity that could be drug-related.

SRC reviews will include, but not limited to, clinical findings, vital signs, hematology and biochemistry results, ECG, AEs, and SAEs. The composition, operation, and management of the SRC will be described in detail in the SRC charter.

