3.6. Stopping and Subjects withdraw Criteria

The following criteria will result in immediate discontinuation of the subject dosing:

- An SAE that is related to GMA301;
- QTcF >500 msec or extension 60 msec against baseline.
- Liver function test abnormalities for severe liver injury (based upon US FDA “Guidance for Industry, Drug-Induced Liver Injury: Premarketing Clinical Evaluation”, July 2009):
 - Alanine aminotransferase (ALT) or aspartate aminotransferase (AST)>3x upper limits of normal (ULN) with total bilirubin > 2X ULN (Hy’s Law)
 - ALT or AST >3x ULN with international normalized ratio (INR)>1.5
 - ALT or AST >8X ULN
 - ALT or AST >5X ULN persisting for more than 2 weeks
 - ALT or AST >3x ULN or 3 times baseline value with the appearance of fatigue, nausea, vomiting, right upper quadrant pain or tenderness, fever, rash and/or eosinophilia (>5%)

Close follow-up of subjects must be organized in any of the above cases including:

- Repeating liver enzyme and serum bilirubin tests 2 or 3 times weekly. Frequency of retesting can decrease to once a week or less if abnormalities stabilize or the trial drug has been discontinued and the subject is asymptomatic.
- Obtaining a more detailed history of symptoms and prior or concurrent diseases
- Obtaining a history of concomitant drug use (including non-prescription medications and herbal and dietary supplement preparations), alcohol use, recreational drug use, and special diets.
- Ruling out acute viral hepatitis types A, B, C, D, and E; autoimmune or alcoholic hepatitis; non-alcoholic steatohepatitis; hypoxic/ischemic hepatopathy; and biliary tract disease.
- Obtaining a history of exposure to environmental chemical agents.
- Obtaining additional tests to evaluate liver function, as appropriate (e.g., INR, direct bilirubin)
- Obtaining gastroenterology or hepatology consultations

If a treatment-related SAE is suspected by investigators, immediate discontinuation of study drug must occur and medical care must be applied and the case immediately reported to the SRC. An ad hoc SRC meeting will be organized to make decisions for the study accordingly.

A subject is free to withdraw from the study at any time. A subject is requested to withdraw by the investigators if any of the following criteria are met:

- Subjects' non-compliance with the study procedure that might affect subject safety or study assessments/objectives, by the investigators

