- Any clinically relevant sign or symptom (eg, Class IV heart failure) that, in the opinion of the Investigator (or designee), warrants subject withdrawal.

Subject who didn't get IMP treatment within protocol defined timeline with any reason can get back to the IMP treatment with investigator or SRC's evaluation and agreement.

All the discontinuation must be documented accordingly. If a subject is withdrawn, the Sponsor will be notified in 24 hours and the date and reason(s) for the withdrawal will be documented in electronic Case Report Form (eCRF). In this case, efforts in any ways must be made to complete the follow up assessments. ([Appendix 6](#)). Other medical procedures may be performed at the Investigator's discretion. The Investigator may also request subjects to return for additional Follow-up visits. All AEs will be followed until recovery or stabilization.

Cohort discontinuation and study termination

The SRC will discontinue or stop the cohort or even the study in case of :

- Two cases discontinuations in a cohort due to events related to the study drug under the diagnosis of the investigators;
- Single case with severe allergic event related to study drug;
- Known and expected AEs are with increased frequency, severity and or long lasting.

The sponsor can terminate the study with notification to the investigators.

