10. APPENDICES

Appendix 1: Adverse Event Reporting

Definitions

An AE is any untoward medical occurrence in a subject or clinical investigation subject administered a pharmaceutical product, which does not necessarily have a causal relationship with this treatment. An AE can therefore be any unfavorable and/or unintended sign (including a clinically significant abnormal laboratory finding), symptom, or disease temporally associated with the use of a study drug, whether or not related to the study drug.

Assessment of Severity

The Investigator will be asked to provide an assessment of the severity of the AE using the following categories:

- **Mild:** event is medically significant but produces no disruption to daily activity;
- **Moderate:** event is medically significant and reduces or affects normal daily activity;
- **Severe:** event is medically significant and results in inability to work or perform normal daily activity.

Relationship to Study drug

The Investigator will make a determination of the relationship of the AE to the study drug using a 4-category system according to the following guidelines:

- **Not Related:** The AE is definitely caused by the subject's clinical state or the study procedure/conditions.
- **Unlikely Related:** The temporal association between the AE and the drug is such that the drug is not likely to have any reasonable association with the AE.
- **Possibly Related:** The AE follows a reasonable temporal sequence from the time of drug administration but could have been produced by the subject's clinical state or the study procedures/conditions.
- **Related:** The AE follows a reasonable temporal sequence from administration of the drug, abates upon discontinuation of the drug, follows a known or hypothesized cause-effect relationship, and (if appropriate) reappears when the drug is reintroduced.

Follow-up of Adverse Events

Every reasonable effort will be made to follow up with subjects who have AEs. Any subject who has an ongoing AE that is possibly related or related to the IMP or study procedures at the Follow-up visit will be followed up, where possible, until resolution or until the unresolved AE is judged by the Investigator (or designee) to have stabilized. This will be completed at the Investigator's (or designee's) discretion. Any

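### The scheduled SRC reviews do not clearly require Cohort 1 early stoppers before 600 mg opens, and omit Cohort 2's last 4 subjects before 1000 mg opens

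*Combined protocol and SAP*

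**What the plan says.** Section 3.5 sets the timing of the SRC meeting and names the subjects whose data it reviews.

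- **Timing.** The committee meets once 8 of 12 subjects have had three doses and 28 days of follow-up, and "the entire cohort of 12 subjects has been randomized".
- **Before 600 mg.** The first meeting reviews "safety data from the initial 8 subjects in Cohort 1 who have completed 3 doses of the study drug" and who have the 28 days of follow-up. Cohort 2 then opens on SRC approval, once the other 4 are randomised.
- **Before 1000 mg.** The second meeting reviews the initial 8 of Cohort 2 and "the 4 residual subjects from Cohort 1 who were not yet reviewed". After approval, "once the residual 4 subjects in Cohort 2 are randomized, Cohort 3 can be initiated for recruitment".
- **Drop-outs.** If 8 or fewer subjects complete and there are some drop-outs, *their* safety data go to the SRC for the escalation decision.
- **Unscheduled review.** In addition, "ad hoc meetings will be organized in case of any SAE or adverse event with maximum severity that could be drug-related".

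The completed-doses qualifier is explicit for Cohort 1 only. For Cohort 2 the text says just the initial 8. The synopsis describes the same two reviews but does not state that all 12 must be randomised before the SRC meets.

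Section 3.6 lists reasons to stop a subject's dosing, among them "QTcF >500 msec or extension 60 msec against baseline". It lets the SRC stop a cohort or the study for "Two cases discontinuations in a cohort due to events related to the study drug under the diagnosis of the investigators", for one severe related allergic event, or for known events that become more frequent, more severe or longer lasting. It also requires that the sponsor hear of a withdrawal within 24 hours.

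**The concern.** The subjects most informative about tolerability are those whose dosing was stopped. A review defined on three-dose completers can leave them out. ECGs are scheduled at Weeks 4 and 8, so a stop for QTcF at either visit, if dosing does not resume, means the subject never becomes a completer.

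The second gap concerns the step to the top dose. Cohort 2's last 4 subjects carry about a third of the 600 mg exposure, and randomisation alone satisfies the condition for opening 1000 mg. Whatever has been seen in them by then need not be tabled.

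Section 3.3 says the sequential design was chosen for safety reasons. The stated review set is narrower than that purpose calls for, and narrower than the data in hand at the meeting.

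**Working it through.** The plan gives no power or formal sample size to reproduce (Section 8.2). Its counts check: 3 × (9 + 3) = 36 and 8 + 4 = 12.

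**1. Scheduled coverage under Section 3.5**

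| Before opening | Cohort 1 | Cohort 2 |
|---|---|---|
| 600 mg | 8 of 12, all completers | – |
| 1000 mg | 12 of 12, if the residual 4 are all those not yet reviewed | 8 of 12 |

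So 12 − 8 = 4 Cohort 2 subjects have no scheduled review before 1000 mg.

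**2. The drop-out sentence.** If completers are counted at the end of the cohort, it needs at least 12 − 8 = 4 non-completers. If they are counted when the SRC meets with exactly 8 completers, one drop-out could be enough. On either count, *their* may mean the completers or the drop-outs. It does nothing for residual subjects still on treatment.

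**3. One example against each safeguard.** Take a lone, asymptomatic QTcF rise above 60 msec.

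- Section 3.6 stops dosing.
- Appendix 1 grades severity by effect on daily activity; mild means "event is medically significant but produces no disruption to daily activity". The case can be graded mild, so the maximum-severity trigger need not fire.
- The SAE trigger fires only if the investigator uses medical judgment to call it an important medical event. That is possible but not certain.
- The two-discontinuation rule is not met by one case.
- The 24-hour notice applies to withdrawal from the study, which is not always the same as stopping dosing.

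**4. GMA301 subjects among Cohort 2's last 4.** Inputs: 9 active and 3 placebo (Section 3.1), random order. With h(k) = C(9,k)·C(3,4−k)/C(12,4) and C(12,4) = 495:

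- k = 1: 9/495 = 0.018
- k = 2: 108/495 = 0.218
- k = 3: 252/495 = 0.509
- k = 4: 126/495 = 0.255
- mean = (9 + 216 + 756 + 504)/495 = 3

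The first 8 therefore hold 5 to 8 on active drug, mean 6.

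**5. Illustrative probabilities.** The documents give no event rates, so p = 5%, 10% and 20% per GMA301 subject are assumptions. Placebo cases are ignored.

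| Quantity | Formula | 5% | 10% | 20% |
|---|---|---|---|---|
| Exactly one related, non-serious stopper among 9 active | 9p(1−p)^8 | 29.9% | 38.7% | 30.2% |
| That stopper is in Cohort 2's last 4, if the initial 8 are the first randomised | previous row × 3/9 | 10.0% | 12.9% | 10.1% |
| At least one AE case in the last 4 | Σ h(k)[1−(1−p)^k] | 14.2% | 26.9% | 48.1% |
| A case in the last 4 and none in the first 8 | Σ h(k)(1−p)^(9−k)[1−(1−p)^k] | 10.5% | 14.6% | 13.1% |
| Same, if 3 of the last 4 are active | (1−p)^6[1−(1−p)^3] | 10.5% | 14.4% | 12.8% |

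If Cohort 2's initial 8 means the first 8 to complete, every lone stopper falls outside the reviewed 8.

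The last three rows credit the residual 4 with their whole event risk. At the cut-off some may only just have been randomised. At each assumed rate, these rows are therefore upper bounds on what adding the residual 4 to the meeting could show.

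**The case against.** The case against is substantial.

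- **Safeguards exist.** Ad hoc meetings, the stopping rules and the 24-hour notice deal with serious, severe or repeated events. The sponsor's and the CRO's lead physicians and 3 investigators sit on the SRC, so members may well know of a stopper. This stands, and it narrows the gap to lone, lesser or judged-unrelated stops and moderate events. Knowing of a case is still not a requirement to review it before escalating.
- **The drop-out sentence may already cover early stoppers.** It can be read that way, which is why the point is that they are not *clearly* required.
- **The residual 4 may simply be the last 4 enrolled.** A reader might infer that a Cohort 1 stopper must fall among the residual 4 and wait for the second meeting. The text allows that reading but does not fix it. An early-enrolled stopper might belong to neither group, leaving the drop-out sentence as the only provision.
- **The SRC charter may say more.** It is not in these documents. Section 3.5 names subjects to be reviewed without barring others. Its open-ended list, however, widens the types of data and not the set of subjects.
- **Early experience was mild.** Section 1.5.1 reports that the most frequent events after single doses up to 1000 mg in healthy subjects needed no intervention. That is relevant, but limited for repeat dosing in PAH.
- **Escalating on a minimum number of completers is deliberate.** Agreed. The count can stay as a timing rule without limiting whose data are seen.

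**Conclusion.** The point holds for the scheduled reviews. As written, a Cohort 1 early stopper is not clearly required in the review before 600 mg, and Cohort 2's last 4 (1 to 4 on 600 mg, mean 3) are in no scheduled review before 1000 mg. The second part is the firmer, because it does not depend on how the drop-out sentence is read.

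Two stronger readings are tempting. One is that early stoppers escape SRC review altogether. The documents do not support this: a possibly drug-related SAE or maximum-severity event brings an ad hoc meeting, and two related discontinuations bring the stopping rule into play. The other is that the percentages are the chance of a missed signal. They are not: they rest on assumed rates, and those for the last 4 assume full follow-up.

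The exposed cases are a single stop that is non-serious and below maximum severity, or judged unrelated, and moderate events in Cohort 2's last 4. Severity is minor to should-fix. The gap is narrow, but it bears directly on opening the next dose and is cheap to close.

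**What to change.** Change Section 3.5, the synopsis and the SRC charter as follows.

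1. State that each scheduled SRC meeting reviews all safety data available at the cut-off from every subject dosed so far in all cohorts. The residual 4 are included with whatever follow-up they have.
2. List early discontinuations individually, with the reason, by subject number and without treatment code, because 3 investigators sit on the committee.
3. Keep the 8-completer count only as the earliest time for the meeting.
4. Reword the drop-out sentence so that the drop-outs' own data are expressly included.
5. Add to the synopsis the Section 3.5 condition that all 12 are randomised before the meeting.

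The cost is a wording change and one extra listing per meeting, with no added visits or subjects. Under Section 3.5 there is no added wait, since all 12 must already be randomised. The synopsis alone would allow an earlier meeting, so item 5 is needed for that to hold throughout. Events in the residual 4 after the cut-off will still rely on the ad hoc meetings and the Section 3.6 stopping rules.

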3.6. Stopping and Subjects withdraw Criteria

The following criteria will result in immediate discontinuation of the subject dosing:

- An SAE that is related to GMA301;
- QTcF >500 msec or extension 60 msec against baseline.
- Liver function test abnormalities for severe liver injury (based upon US FDA “Guidance for Industry, Drug-Induced Liver Injury: Premarketing Clinical Evaluation”, July 2009):
 - Alanine aminotransferase (ALT) or aspartate aminotransferase (AST)>3x upper limits of normal (ULN) with total bilirubin > 2X ULN (Hy’s Law)
 - ALT or AST >3x ULN with international normalized ratio (INR)>1.5
 - ALT or AST >8X ULN
 - ALT or AST >5X ULN persisting for more than 2 weeks
 - ALT or AST >3x ULN or 3 times baseline value with the appearance of fatigue, nausea, vomiting, right upper quadrant pain or tenderness, fever, rash and/or eosinophilia (>5%)

Close follow-up of subjects must be organized in any of the above cases including:

- Repeating liver enzyme and serum bilirubin tests 2 or 3 times weekly. Frequency of retesting can decrease to once a week or less if abnormalities stabilize or the trial drug has been discontinued and the subject is asymptomatic.
- Obtaining a more detailed history of symptoms and prior or concurrent diseases
- Obtaining a history of concomitant drug use (including non-prescription medications and herbal and dietary supplement preparations), alcohol use, recreational drug use, and special diets.
- Ruling out acute viral hepatitis types A, B, C, D, and E; autoimmune or alcoholic hepatitis; non-alcoholic steatohepatitis; hypoxic/ischemic hepatopathy; and biliary tract disease.
- Obtaining a history of exposure to environmental chemical agents.
- Obtaining additional tests to evaluate liver function, as appropriate (e.g., INR, direct bilirubin)
- Obtaining gastroenterology or hepatology consultations

If a treatment-related SAE is suspected by investigators, immediate discontinuation of study drug must occur and medical care must be applied and the case immediately reported to the SRC. An ad hoc SRC meeting will be organized to make decisions for the study accordingly.

A subject is free to withdraw from the study at any time. A subject is requested to withdraw by the investigators if any of the following criteria are met:

- Subjects' non-compliance with the study procedure that might affect subject safety or study assessments/objectives, by the investigators
- Any clinically relevant sign or symptom (eg, Class IV heart failure) that, in the opinion of the Investigator (or designee), warrants subject withdrawal.

Subject who didn't get IMP treatment within protocol defined timeline with any reason can get back to the IMP treatment with investigator or SRC's evaluation and agreement.

All the discontinuation must be documented accordingly. If a subject is withdrawn, the Sponsor will be notified in 24 hours and the date and reason(s) for the withdrawal will be documented in electronic Case Report Form (eCRF). In this case, efforts in any ways must be made to complete the follow up assessments. ([Appendix 6](#)). Other medical procedures may be performed at the Investigator's discretion. The Investigator may also request subjects to return for additional Follow-up visits. All AEs will be followed until recovery or stabilization.

Cohort discontinuation and study termination

The SRC will discontinue or stop the cohort or even the study in case of :

- Two cases discontinuations in a cohort due to events related to the study drug under the diagnosis of the investigators;
- Single case with severe allergic event related to study drug;
- Known and expected AEs are with increased frequency, severity and or long lasting.

The sponsor can terminate the study with notification to the investigators.

